#### 6.3.2. Secondary Endpoints: Immunogenicity

**For part A**: The principal immunogenicity endpoints will be assessed by evaluation of HA specific responses to VRC-FLUMOS0111-00-VP and Flucelvax® at Week 2 (Visit 04) after vaccination.

**For part B** and **C**: The principal immunogenicity endpoints will be assessed by evaluation of HA specific responses to VRC-FLUMOS0111-00-VP alone or VRC-FLUMOS0111-00-VP with Adjuplex at Week 2 (Visit 04) after vaccination.

#### 6.3.3. Exploratory Endpoints: Immunogenicity

Exploratory immunogenicity evaluations may include the detection of antibody by MSD or similar platform, microneutralization assay, and exploratory B and T cell assays.

#### 6.3.4. Sample Size Consideration for Safety

**For part A**: Group 1A-1B (*dose-escalation*) with sample size n=5, there is over 90% chance to observe at least 1 SAE if the true rate is at least 37% and over 90% chance to observe no SAE if the true rate is no more than 2%. For Groups 2A-2B and 3A-3B with each group of size n=15, there is over 90% chance to observe at least 1 SAE if the true rate is at least 14.3% and over 90% chance to observe no SAE if the true rate is no more than 0.6%.

For **Part B** and **Part C**, with sample size n=13, there is over 90% chance to observe at least 1 SAE if the true rate is at least 16.3% and over 90% chance to observe no SAE if the true rate is no more than 0.8%.

Probabilities of observing 0 or more than 1 SAE within a group are presented in **Table 2** for a range of possible true event rates.

True Event	n=5 in a group		n=15 in a group		n=13 in a group	
Rate	Pr(0)	Pr(>1)	Pr(0)	Pr(>1)	Pr(0)	Pr(>1)
0.005	0.975	0	0.928	0.003	0.937	0.002
0.01	0.951	0.001	0.86	0.01	0.878	0.007
0.02	0.904	0.004	0.739	0.035	0.769	0.027
0.035	0.837	0.011	0.586	0.095	0.629	0.074
0.05	0.774	0.023	0.463	0.171	0.513	0.135
0.1	0.59	0.081	0.206	0.451	0.254	0.379
0.15	0.444	0.165	0.087	0.681	0.121	0.602
0.2	0.328	0.263	0.035	0.833	0.055	0.766
0.3	0.168	0.472	0.005	0.965	0.01	0.936

**Table 2: Probability of Observing Events under Different Scenarios** 

**Table 3** gives the upper and lower bounds for 95% exact binomial confidence intervals of the true SAE rate at possible numbers of events within a group. Within a group of size n=5, if none experience an SAE, the 95% exact confidence interval has upper bound 0.522. Within a group of size n=15, if 2 enrollees experience an SAE, the exact 95% confidence interval has lower bound 0.017 and upper bound 0.405. Within a group of size n=13, if 2 enrollees experience SAE, the exact 95% confidence interval has lower bound 0.019 and upper bound 0.454.

## Table 3: 95% Confidence Intervals for the True Rate under Possible Observed Number of Events

Observed Number	95% Confidence	95% Confidence	95% Confidence
of Events	Interval	Interval	Interval

	(n=5)		(n=15)		(n=13)	
	Lower	Upper	Lower	Upper	Lower	Upper
	Bound	Bound	Bound	Bound	Bound	Bound
0	0	0.522	0	0.218	0	0.247
1	0.005	0.716	0.002	0.319	0.002	0.36
2	0.053	0.853	0.017	0.405	0.019	0.454
3	0.147	0.947	0.043	0.481	0.05	0.538
4	0.284	0.995	0.078	0.551	0.091	0.614
5	0.478	1	0.118	0.616	0.139	0.684
6			0.163	0.677	0.192	0.749
7			0.213	0.734	0.251	0.808

#### 6.3.5. Sample Size Consideration for Immunogenicity

**Table 3** also applies to the sample size consideration for immunogenicity. Within a group of size n=15, if there are two positive responders with respect to an immunogenicity endpoint, the 95% confidence interval of the positive response rate has the lower bound of 0.017 and the upper bound of 0.405. Within a group of size n=13, if there are two positive responders with respect to an immunogenicity endpoint, the 95% confidence interval of the positive response rate has the lower bound of 0.019 and the upper bound of 0.454.

## 6.4. Statistical Analysis

All statistical analyses will be performed using Statistical Analysis System (SAS) (SAS Institute, Cary, NC), R, or S-Plus statistical software. No formal multiple comparison adjustments will be employed for safety endpoints or secondary endpoints.

#### 6.4.1. Analysis Variables

The analysis variables consist of baseline variables and safety variables for primary and secondary objective analyses.

#### 6.4.2. Baseline Demographics

Baseline characteristics including demographics and laboratory measurements will be summarized using descriptive statistics.

#### 6.4.3. Safety Analysis

#### 6.4.3.1 Solicited Reactogenicity

The number and percentage of participants experiencing each type of reactogenicity sign or symptom will be tabulated by severity. For a given sign or symptom, each participant's reactogenicity will be counted once under the maximum severity for all assessments.

#### 6.4.3.2 Adverse Events

AEs are coded into Medical Dictionary for Regulatory Activities (MedDRA) preferred terms. The number and percentages of participants experiencing each specific AE will be tabulated by severity and relationship to treatment. For the calculations in these tables, each participant's AE will be counted once under the maximum severity or strongest recorded causal relationship to treatment.

A complete listing of AEs for each participant will provide details including severity, relationship to treatment, onset, duration and outcome.

#### 6.4.3.3 Local Laboratory Values

Boxplots, violin plots, or beeswarm plots of local laboratory values will be generated for baseline values and for values measured during the course of the study. Each plot will show the 1st quartile, the median, and the 3rd quartile. Outliers, or values outside the boxplot, will also be plotted. If appropriate, horizontal lines representing boundaries for abnormal values will be plotted.

#### 6.4.4. Immunogenicity Analysis

The statistical analysis for immunogenicity will employ the intent-to-treat principle whereby all data from enrolled subjects will be analyzed according to the group assignment. If needed, a perprotocol analysis will be performed as secondary analysis where subjects will be analyzed according to their actual vaccination scheme if it is different from the assigned or up to the last visit in the study if there are early dropouts.

If assay data are qualitative (i.e., positive or negative) then analyses will be performed by tabulating the frequency of positive response for each assay at each time point that an assessment is performed. Binomial response rates will be presented with their corresponding exact 95% confidence interval estimates.

Some immunologic assays have underlying continuous or count-type readout that is often dichotomized into responder/non-responder categories. For these assays, graphical and tabular summaries of the underlying distributions will be made. These summaries may be performed on transformed data (e.g., log transformation) for ease of interpretation.

#### 6.4.5. Missing Data

Missing responses will be assumed to be missing completely at random. Analyses will include all samples available at each study time point. Based on experience from previous trials, we expect missing data to be rare. Regardless, in the event of missing data, we will report the occurrence and extent of missingness. We will also provide plausible explanations for the missingness mechanism, should such information be available.

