## **1.8.** Assessment of Vaccine Immunogenicity

In this study, specimens to evaluate immunogenicity will be collected at baseline and at specified time points. The primary immunogenicity time point is two weeks after product administration. The immunogenicity will be assessed by detection of HA responses to influenza H1, H3, HBv, and Hby HA strains using the Meso-Scale Discovery (MSD) or similar platform.

Additional assessment of HA specific antibody responses may be conducted on stored samples obtained throughout the study.

Exploratory evaluations may include measurements of antibody response to the engineered pentameric scaffold of lumazine synthase from *C. albicans* and engineered trimer at various time points throughout the study.

Additional exploratory evaluations may include the detection of neutralizing antibodies to influenza by neutralization and functional serological assays, and exploratory B and T cell assays.

Research sample processing prior to immunogenicity testing will be performed by the Vaccine Immunology Program (VIP) in Gaithersburg, MD, which will also perform some of the immunogenicity assays.

Some immunogenicity assays may be performed by the VRC laboratories in Bethesda, MD, or by approved contract laboratories or research collaborators.

Results from this study are expected to contribute to the fund of knowledge needed for the development of a universal influenza vaccine candidate as well as to show proof-of-concept for elicitation of antibody responses by a quadrivalent mosaic vaccine and contribution of a novel adjuvant, Adjuplex, to vaccine immunogenicity.

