# **3.3.** Exploratory Objectives

- To evaluate the specificity and functionality of VRC-FLUMOS0111-00-VP and Flucelvax® vaccine-induced antibodies and the immune response at various timepoints throughout the study.
- To evaluate the frequency, magnitude, phenotype, and specificity of HA-specific B-cell, T-cell, and antibody responses at various time points throughout the study.
- To evaluate the antibody response to the pentameric scaffold lumazine synthase and engineered trimer at various time points throughout the study.

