## 4.4.4. Screening

All screening procedures for this study will be completed through the VRC's screening protocol, VRC 500 (NIH 11-I-0164, NCT01375530) used for all VRC IND studies conducted at the NIH Clinical Center. The evaluations and sample collections included in screening are a medical

history, physical exam, laboratory tests needed to confirm eligibility, HIV, and pregnancy test for females of reproductive potential.

If screening evaluations suggest a current concerning health condition or infection, then appropriate laboratory tests may be conducted to evaluate these conditions under screening protocol, VRC 500. Additional assessments of health may be conducted during screening based on clinical judgment. Screening evaluations for specific eligibility criteria (Section 4.2) must be completed within the time interval specified prior to enrollment for the given parameter and may be repeated, as needed, to confirm eligibility. No screening procedures will be done under protocol VRC 325.

Research blood samples may be collected at any time during screening through enrollment and will not be subject to the "56-day prior to enrollment" restriction.

Subjects who are not up to date on standard vaccinations may receive these, if available, during their participation in the screening protocol or at a later date during study participation.

The informed consent form (ICF) will be reviewed and counseling related to pregnancy prevention will be provided. As part of the informed consent process, an Assessment of Understanding (AoU) will be completed in association with enrollment into VRC 325. Records will be kept documenting the reason if screened subjects do not enroll.

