#### 4.4.16. Concomitant Medications

Routine prescription medications in use at the time of enrollment will be entered in the database. Subsequently, the concomitant medications that will be recorded or updated in the database are those associated with an AE requiring expedited reporting or the development of a new chronic condition requiring ongoing medical management. Anti-viral medications taken during influenza or influenza-like illnesses will be recorded in the database. Receipt of an FDA-approved vaccine at any time during the study will be recorded in the database (clinicians should work with subjects regarding the timing of licensed vaccines relative to study injection). Inclusion of other concomitant medications in the database may also be determined at the discretion of the PI. Otherwise, concomitant medications taken throughout the study will be recorded in the subject's study chart and general medical record but will not be recorded in the database.

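### Exploratory HA-specific summaries after Week 2 do not separate samples taken after a recorded licensed influenza vaccine or PCR-confirmed influenza: a cheap, low-priority addition

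*Combined protocol and SAP*

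**What the plan says.** **Analysis rule.** Section 6.4.4 applies the intent-to-treat principle, so "all data from enrolled subjects will be analyzed according to the group assignment". Section 6.4.5 adds: "Analyses will include all samples available at each study time point". For positive/negative assays, Section 6.4.4 says: "If assay data are qualitative (i.e., positive or negative) then analyses will be performed by tabulating the frequency of positive response". For continuous or count readouts, "graphical and tabular summaries of the underlying distributions will be made". The only alternative set is a conditional per-protocol analysis, for a vaccination that differs from the assigned one or for early dropout.

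**Late HA readouts.** Section 3.3 lists as exploratory the "specificity of HA-specific B-cell, T-cell, and antibody responses at various time points throughout the study". Section 1.8 says: "Additional assessment of HA specific antibody responses may be conducted on stored samples obtained throughout the study". Appendix I schedules serum and PBMC at six visits after Week 2: Weeks 4, 12, 16, 22, 28 and 40.

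**Outside exposure.** Section 4.4.16 states: "Receipt of an FDA-approved vaccine at any time during the study will be recorded in the database". Section 5.1 has influenza and influenza-like illness (ILI) recorded to the last visit, with a swab and PCR for participants who meet the ILI criteria. Section 4.4.11 runs follow-up to 40 weeks and through an influenza season. Section 4.4.4 says that participants who are behind on standard vaccinations "may receive these, if available, during their participation in the screening protocol or at a later date during study participation"; it does not name influenza vaccine.

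**The concern.** A late HA-specific response in a trial participant can come from the study injection, from a later licensed influenza vaccine, or from influenza itself. The plan collects what is needed to tell recorded outside exposures apart from the rest, but no analysis uses it. A Week 28 or Week 40 summary by group would mix these sources, and no planned table would show how many participants had been exposed by then.

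What is at stake is how late summaries are read. No objective names persistence. However, Section 1.2 presents the vaccine as possibly giving durable protection, and Section 1.3 lists durability among the things adjuvants improve, so late HA levels may be taken as evidence of it.

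**Working it through.** **1. Is any separation planned?** The statistical section (Section 6) contains three relevant rules: analysis by assigned group, all available samples, and the conditional per-protocol set. In the last, the actual vaccination is set against the assigned one, so it refers to the study vaccination. It has no rule for samples taken after an outside exposure. None of the three separates such samples.

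**2. What partial handling exists?**

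| Step | What it does | What it leaves open |
|---|---|---|
| Exclusions 10 and 11 (4.2.2) | Named seasons' vaccine (2020-2021 in Part A; 2021-2022 or 2022-2023 in Part B) excluded at any time before enrolment in the A subgroups, within 4 months in the B subgroups | Acts before Day 0 only; inclusion criteria 3 and 4 (4.2.1) require at least one licensed influenza vaccine in an earlier specified period |
| Clinicians advise on licensed-vaccine timing (4.4.16) | Can also affect vaccines given after Day 0 | Does not separate samples |
| Enrolment balance, Groups 4 and 5 (4.5) | Aims at similar community exposure | Does not cover Groups 1-3 or split sources within a group |
| Adverse event listing (6.4.3.2) | May show some influenza or ILI cases with onset | No table of licensed-vaccine receipt; no exposure count by group and visit |

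**3. Do late visits fall in plausible exposure periods?** Inputs are the accrual dates in Section 1.5.1 (Part A 24 May to 17 August 2021; Part B 6 September 2022 to 20 April 2023) and the Appendix I visit days. Nominal date = accrual date + 84, 196 or 280 days, ignoring visit windows. The early dates are lower bounds, because they start from the opening of accrual and not from a first injection.

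| | Week 12 (+84) | Week 28 (+196) | Week 40 (+280) |
|---|---|---|---|
| Part A | 16 Aug - 9 Nov 2021 | 6 Dec 2021 - 1 Mar 2022 | 28 Feb - 24 May 2022 |
| Part B | 29 Nov 2022 - 13 Jul 2023 | 21 Mar - 2 Nov 2023 | 13 Jun 2023 - 25 Jan 2024 |

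Follow-up in both parts spans autumn and winter, as Section 4.4.11 intends. In Part B, Week 4 samples (4 October 2022 to 18 May 2023) could also be affected.

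**4. How large could the effect be?** The plan gives no exposure rate or titre rise, so there is no figure of its own to reproduce on this point. As an illustration, assume k of n participants are exposed, each with an F-fold rise and no waning. On the log scale:

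inflation of the geometric mean = F^(k/n)

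| n | k | F = 2 | F = 4 |
|---|---|---|---|
| 13 | 1 | 2^(1/13) = 1.05 | 4^(1/13) = 1.11 |
| 13 | 3 | 2^(3/13) = 1.17 | 4^(3/13) = 1.38 |
| 15 | 1 | 2^(1/15) = 1.05 | 4^(1/15) = 1.10 |
| 15 | 3 | 2^(3/15) = 1.15 | 4^(3/15) = 1.32 |
| 5 | 1 | 2^(1/5) = 1.15 | 4^(1/5) = 1.32 |

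For two groups of equal size n, the between-group ratio shifts by F^((k1 - k2)/n). It does not move when exposure and rise are equal.

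**5. Positive/negative assays.** Table 3 gives exact 95% intervals for n = 13, and recomputation agrees: 2/13 = 15.4% (0.019-0.454), 3/13 = 23.1% (0.050-0.538), 4/13 = 30.8% (0.091-0.614). If one or two participants were positive solely through outside exposure, 2/13 would become 3/13 or 4/13. The intervals overlap heavily.

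**The case against.** The strongest reply is that this is a refinement and not an error. Week 2 is the principal immunogenicity time point and the only one named in the secondary objectives. Later HA assays are optional and descriptive, and the durability language is background text. An all-samples summary by assigned group is a legitimate description. The restricted set is not clearly better: it is smaller, it is selected on events after vaccination, and it still contains infections that never met the ILI criteria. All of this stands, and it sets the priority low. It does not remove the gap, because the all-samples summary would be kept and the second would only be read beside it.

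A reader might infer more than the documents support:

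- *That Section 6.4.5 forbids a separate summary.* It is an available-case rule for missing data. The gap is only that no such summary is planned.
- *That the protocol expressly provides for influenza vaccination during follow-up.* Section 4.4.4 speaks of standard vaccinations, and Section 4.4.16 shows recording, not frequency.
- *That participants in the A subgroups had no prior influenza vaccine.* Only the named seasons are excluded, and an earlier licensed vaccine is required.
- *That outside exposure would be invisible.* Influenza and ILI cases may partly appear in the adverse event listing. The gap is firmer for licensed-vaccine receipt.

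**Conclusion.** The concern holds as a cheap improvement of low priority. For exploratory HA-specific readouts after Week 2, mainly Weeks 12 to 40, the plan summarises all available samples by assigned group. It neither separates nor counts those taken after a recorded licensed influenza vaccine or PCR-confirmed influenza. Existing measures limit or balance exposure, but none separates the two sources of a late response.

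It would be too strong to say that the late results are biased. The documents give no exposure count, and every magnitude above rests on an assumed number exposed, an assumed 2- to 4-fold rise and no waning. With one exposed participant in a group of 13 or 15 the effect is small (1.05- to 1.11-fold). With three of 13 it is 1.17- to 1.38-fold. The imprecision of small groups remains the larger limit.

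Nor does the point reach the main results. The Week 2 endpoints leave only about 14 days for outside exposure, and the safety endpoints are not HA readouts, so both are essentially unaffected. Antibody to the lumazine synthase scaffold is outside the point.

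**What to change.** In Sections 6.4.4 and 6.4.5, for HA-specific time points after Week 2:

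1. Keep the all-samples summary by assigned group.
2. Report the number of participants exposed by each visit, by group, separately for licensed influenza vaccine and PCR-confirmed influenza.
3. Add a sensitivity summary that omits each participant's HA samples after the first such recorded exposure.
4. Read any statement on late or persistent responses in light of both summaries, not the restricted one alone.
5. State the limits: smaller n, selection on post-vaccination events (which may remove weaker responders), and undetected infections that stay in the restricted set.

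**Cost.** SAP wording, one flag derived from data already recorded, one count and one extra table. Sample size and power do not change. The restricted summary is less precise: the 95% half-width of a group mean in SD units is t/√n, so going from 13 to 10 participants widens it from 2.179/√13 = 0.60 to 2.262/√10 = 0.72.

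**Timing.** The last nominal Week 40 visit was about 25 January 2024, version 7.0 is dated 11 February 2025, and Section 6.4.6 lets exploratory assays be analysed as data arrive. If late results by group have already been seen, label the summary post hoc.

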#### 6.4.6. Interim Analyses

**Safety Reviews:** The PSRT will review safety data routinely throughout the study. The study will utilize both electronic database features and reviews by designated safety review personnel to identify in a timely manner if any of the safety pause rules of the study are met.

**Immunogenicity Review:** Analyses of immunogenicity may be performed by neutralization assay of samples collected 2 weeks after vaccination. This may occur prior to completion of safety follow-up visits or collection of data for secondary and exploratory immunogenicity endpoints. Such an analysis would constitute the final analysis for the primary immunogenicity endpoint, so sample size adjustments are not required. Reports providing results by study group may be provided to VRC solely for the purpose of informing decisions related to future trials in a timely manner. The results should in no way influence the conduct of the VRC 325 trial in terms of early termination or later safety or immunogenicity endpoint assessments. Analyses of secondary and exploratory immunogenicity assays may also be performed as data become available.

## 7. PHARMACY AND VACCINE ADMINISTRATION PROCEDURES

The study groups and study agent dosing schedule are shown in **Table 1** in Section 4.1.

## 7.1. Study Products

Investigational vaccine:

VRC-FLUMOS0111-00-VP is a sterile aqueous buffered solution aseptically filled into 3 mL single-dose glass vials. Each vial contains 0.7 ± 0.1 mL at a concentration of 180 ± 18 mcg/mL in formulation buffer composed of 20mM acetate phosphate, 30 mM NaCl, 5% w/v sucrose, 2.5% w/v sorbitol, 0.01% w/v Pluronic F-68, pH 5.7. Vials are intended for single use only and do not contain preservative. Vials must not be refrozen after thawing.

Licensed Comparator QIV Flucelvax®:

- Flucelvax® is a sterile, slightly opalescent suspension in phosphate buffered saline for IM injection supplied in a 0.5 mL single-dose in a pre-filled Luer Lock syringe and is formulated to contain a total of 60 micrograms (mcg) of H1, H3, HBv, and HBy HA strains per 0.5-mL dose, in the recommended ratio of 15 mcg HA for each of the four influenza strains.
- Flucelvax® contains no adjuvants, preservatives or antibiotics. Syringes must be refrigerated at the recommended storage condition at 2°C to 8°C. Do not freeze and protect from light. Do not use after the expiration date.

Adjuvant:

- Adjuplex Adjuvant (VRC-GENADJ0110-AP-NV): is provided as 3-mL single-use glass vials with a fill volume of 0.7 mL. Each vial contains an off-white, semi-opaque (not transparent), preservative-free, sterile liquid with no visible particles and which is homogenous after a gentle shake.
- Adjuplex is mixed with vaccine in the pharmacy during preparation. prior to vaccination to maintain a 20% (v/v) dose of Adjuplex.

